3.3.1 Inclusion Criteria

1. Histopathologically proven prostate adenocarcinoma.
2. Rising PSA (at least two consecutive rising PSAs) after definitive therapy with prostatectomy or radiation therapy (external beam or brachytherapy).
 - a. Post radical prostatectomy (RP) – AUA recommendation for biochemical recurrence after radical prostatectomy
 - i. PSA greater than or equal to 0.2 ng/mL measured more than 6 weeks after RP.

- b. Post-radiation therapy –ASTRO-Phoenix consensus definition of biochemical recurrence after radiation therapy
 - i. Nadir + greater than or equal to 2 ng/mL rise in PSA
3. Karnofsky performance status of ≥ 50 (or ECOG/WHO equivalent).
4. Age > 18.
5. Ability to understand a written informed consent document, and the willingness to sign it.

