6.1.1.1 Screening Assessments

The Screening procedures and assessments must be completed within 30 days of the day 1 Visit.

- Laboratory values: all patients must have a recent PSA (within 30 days prior to study enrollment) consistent with BCR
 - If only one PSA greater than or equal to 0.2 ng/dL post radical prostatectomy is available, then a second confirmatory PSA must be checked prior to the ⁶⁸Ga-PSMA-11 PET study.
- Pathology: all patients must have histopathology/biopsy of the prostate with a documented Gleason score
- Performance status: all patients must have their Karnofsky performance status (or ECOG/WHO equivalent) evaluated (Appendix 1).
- Change in management: A pre-imaging survey of planned clinical management will be performed prior to ⁶⁸Ga PSMA-11 PET/CT imaging.

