8.3.2 Analysis of Primary Endpoints

Sensitivity on a per-patient and per-region-basis of ^{68}Ga -PSMA-11 PET for detection of tumor location confirmed by histopathology/biopsy, clinical and conventional imaging follow-up will be calculated and reported along with the corresponding two-sided 95% confidence intervals. The confidence intervals will be constructed using the Wilson score method. For successful completion of the primary endpoint, two of the three readers will need to have an 70% sensitivity for the detection of disease on a per patient level for the cases that have a) imaging follow-up, b) pathology correlation or c) combination of pathology and imaging follow-up and/or pathology correlation.

^{68}Ga -PSMA-11 PET Results Definition

a) Imaging interpretation ^{68}Ga -PSMA-11 PET:

Local Interpretations: PET images will initially be interpreted by a board certified nuclear medicine physician or a board-certified radiologist experienced in reading PET at the time of the imaging study at the institution that the study is being performed. These interpretations will not be used for final evaluation, and will not be reported as part of the primary or secondary endpoints.

Central Read Logistics: Imaging data will be anonymized and collected at a central site. PET data will be interpreted by three different readers in a random order at separate reading sessions. Cross sectional imaging (CT or MRI) from the ^{68}Ga -PSMA-11 PET will be available for anatomic correlate. The Central readers will be blinded to all other imaging results and all other clinical data.

Reader Positivity and Negativity Definition: Regions defined in Table 1 will be graded for the presence of suspected disease on a two-point scale by each reader (0=Negative or 1=Positive). A region will be judged as positive if at least one lesion in this region is visually positive.

Reader Training: ^{68}Ga -PSMA-11 PET/CT reading training set and guides will be provided and completion of this training will be required for all central review readers. Common pitfalls will be reviewed as part of the reader training.

Criteria for visual interpretation:

Regions of suspected disease will be graded on a two-point scale by each blinded reader (0=Negative or 1= Positive). A region will be judged as positive if at least one lesion in this region is visually positive.

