- (2) True negative patient: in the absence of True Positive or False Positive lesions, a patient will be considered a True Negative if there is pathology that is negative for disease and corresponding lesion is negative by PSMA PET.
 - (3) False positive patient:
 - (a) Pathology confirms a false positive lesion that is read as positive on PSMA PET.
 - (b) In the absence of pathology: there are no true positive regions, and there is a region that is categorized as false positive based on imaging or clinical follow-up.
 - (4) False negative patient: in the absence of True Positive or False Positive lesions, a patient will be considered a False Negative if there is pathology that is positive for disease and corresponding lesion is negative by PSMA PET. Additionally, patients without evidence of disease on PSMA PET but with biochemical evidence of disease will be considered a False Negative.
- ii) Region level evaluation: Each patient will have four evaluable regions (Table 1: prostate bed, pelvis, extrapelvic soft tissue, and bone metastases). Each region will be categorized as true positive or false positive as described above. Regions without evidence of PSMA positive disease or deemed inevaluable will not be included in the analysis.
 - (1) True positive region:
 - (a) Pathology confirms a PSMA avid lesion as a true positive in the region.
 - (b) In the absence of pathology, clinical or imaging follow-up demonstrates a true positive lesion within the region independent of the presence of an inevaluable lesion or a false positive lesion
 - ie true positive disease will supersede a false positive lesion in the region based analysis if based on imaging/clinical follow-up
 - (2) True negative region: in the absence of True Positive or False Positive lesions within a region, the region will be considered a True Negative if there is pathology that is negative for disease in the region and corresponding lesion is negative by PSMA PET.
 - (3) False positive region:
 - (a) Pathology confirms a PSMA avid lesion as a false positive in the region

- (b) In the absence of pathology, there are no true positive lesions in the region, and there is a false positive lesion by clinical or imaging follow-up.
- (4) False negative region: in the absence of True Positive or False Positive lesions in a region, the region will be considered a False Negative if there is pathology that is positive for disease in the region and corresponding lesion is negative by PSMA PET.

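### A man whose only PSMA-positive finding is classed false positive leaves the per-patient sensitivity denominator, while a PET-negative man with the same biochemical recurrence counts as a miss

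*Combined protocol and SAP*

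**What the plan says.** Everyone enrolled has biochemical recurrence. Section 3.3.1 requires "Rising PSA (at least two consecutive rising PSAs) after definitive therapy", and section 6.1.1.1 adds that "all patients must have a recent PSA (within 30 days prior to study enrollment) consistent with BCR".

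Section 8.3.2 d) i) then sorts patients for each blinded reader:

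- **False negative.** There is a pathology route: "in the absence of True Positive or False Positive lesions, a patient will be considered a False Negative" if pathology shows disease at a site that PET read as negative. There is also a biochemical route: "Additionally, patients without evidence of disease on PSMA PET but with biochemical evidence of disease will be considered a False Negative".
- **False positive.** Either pathology refutes a PET-positive lesion or, without pathology, "there are no true positive regions, and there is a region that is categorized as false positive based on imaging or clinical follow-up".
- **True positive.** One true-positive region is enough, unless pathology has classed another region as false positive. In that case the pathology result prevails over regions confirmed only by imaging or clinical follow-up.

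The success rule, also in 8.3.2, is that "two of the three readers will need to have an 70% sensitivity for the detection of disease on a per patient level", among cases with imaging follow-up, pathology or both. It sets no condition on false positives. PPV is a secondary endpoint (8.3.3), reported separately for each reader. The sensitivity formula is not written out, and no text places false-positive patients in its denominator.

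**The concern.** Leaving false positives out of a sensitivity denominator is right when they are free of disease. Here the plan itself takes biochemical recurrence as sufficient evidence of disease, because that is what makes a PET-negative man a miss. A man whose only PET-positive finding is classed false positive has the same recurrence, and the objective in section 2.1 is to detect tumor location, which PET did not do for him on this classification. He cannot be a false negative: the pathology route is closed to anyone with a false-positive lesion, and the biochemical route needs a negative PET.

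The two kinds of failure are therefore treated differently. A negative read lowers the measure, and a refuted positive read removes the man from it. A reader with a lower visual threshold can move men from the first group to the second and gain on the success criterion without locating any more disease. The 70% verdict, in a trial meant to support a marketing application (section 1.1), could then depend partly on reader threshold.

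**Working it through.** **1. Inputs**

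- PET-negative share: 24% (8.2.1), so 76% are PET-positive. The four listed site shares add to 77%; the difference is rounding.
- Evaluable patients: 375 (8.2.1).
- Confirmed share of PET-positive men: 87%, an assumption. Section 8.2.1 calls this figure specificity, but it comes from biopsies with no true negatives, so it is used here as the share of positives confirmed. A range is shown.
- Assumed: all 375 are classed TP, FP or FN (full verification), and sensitivity is TP/(TP+FN).

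**2. The plan's own sample size**

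n = [(2.326 × √(0.5 × 0.5) + 1.282 × √(0.7 × 0.3)) / 0.2]² = 76.6, so 77, against the stated 75. The other figures follow: 75/0.20 = 375 and 75/0.70 = 107.

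**3. Two denominators**

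FN = 0.24 × 375 = 90, PET-positive = 285, and TP = confirmed share × 285.

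| Confirmed share | TP | FP | As written: TP/(TP+90) | FP-only men counted: TP/375 |
|---|---|---|---|---|
| 70% | 200 | 85 | 200/290 = 69.0% | 53.3% |
| 80% | 228 | 57 | 228/318 = 71.7% | 60.8% |
| 87% | 248 | 37 | 248/338 = 73.4% (Wilson 68.4 to 77.8) | 66.1% (61.2 to 70.7) |
| 95% | 271 | 14 | 271/361 = 75.1% | 72.3% |

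**4. Where the 70% verdict differs**

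With s the confirmed share:

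- As written: 0.76s/(0.76s + 0.24) ≥ 0.70 requires 0.76s ≥ 0.56, so s ≥ 56/76 = 73.7%.
- With FP-only men counted: 0.76s ≥ 0.70, so s ≥ 70/76 = 92.1%.

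Between these values the handling decides the 70% rule. Below 73.7% both versions fail, and above 92.1% both pass.

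**5. Effect of a lower reading threshold**

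Start from 248 TP, 37 FP and 90 FN. Suppose k of the 90 negatives become positive calls that are later refuted. Written sensitivity is 248/(338 − k) and PPV is 248/(285 + k).

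- k = 9: 248/329 = 75.4%, PPV 84.4%.
- k = 22: 248/316 = 78.5%, PPV 80.8%.
- k = 45: 248/293 = 84.6%, PPV 75.2%.

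Correct detection stays at 248/375 = 66.1% throughout. As an extreme case, a reader who locates disease in 188 of 375 men (50%, the null value) reaches 188/268 = 70.1% if 107 of the other 187 receive a refuted call. PPV is then 188/295 = 63.7%.

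**6. Effect in the other direction**

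If pathology refutes an extra call in men who are TP by imaging only, they become false-positive patients. Moving 10 gives 238/328 = 72.6%, and moving 25 gives 223/313 = 71.2%, against 73.4%.

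**7. The inevaluable route**

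If the 45 extra calls in step 5 end as inevaluable rather than refuted, those men leave both denominators. The version that counts FP-only men then becomes 248/(375 − 45) = 75.2%.

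**8. The formal test**

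At 248/375 the Wilson lower limit is 61.2%. At the plan's per-patient size of 107 (26 negative, 81 positive, 70 TP), 70/107 = 65.4% and z = (0.654 − 0.5)/√(0.25/107) = 3.19, above the one-sided 0.01 critical value of 2.33. The null of at most 50% is rejected either way.

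**The case against.** The strongest objection is that TP/(TP+FN) is the ordinary definition of sensitivity and the alternative is really a correct-detection rate. This does not succeed here, because the plan's own false-negative rule treats every enrolled man as diseased. It is still a reason to report both versions.

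Over-calling is also constrained and visible. Central readers are blinded and trained, uptake criteria are defined, and PPV is reported for each reader. That stands, but PPV cannot change the primary verdict.

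Three further objections stand and limit the point:

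- **Not every false-positive label is a refutation.** Under 8.3.2 b), a site can be classed false positive because PSA did not fall by more than 50% after targeted treatment. A correctly located lesion with further disease elsewhere could meet that rule. A reader might infer that all these men's calls were proven wrong; the documents do not support that.
- **Some wrong calls would end as inevaluable.** An untreated nodal, visceral or prostate-bed lesion is false positive only if it shrinks by a set amount, and a lesion meeting neither set of criteria drops out. Changing only the handling of false positives leaves this route open (step 7).
- **Over-calling does not always raise the measure.** Step 6 shows the opposite effect. The upward effect concerns men who would otherwise be read negative.

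**Conclusion.** The asymmetry is in the text and nothing elsewhere in the plan corrects it. At patient level, the level of the success rule, a refuted call replaces a miss with an exclusion. In the illustration the gap is 7.3 percentage points (73.4% against 66.1%), with the 70% threshold between the two figures.

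A reader might go further and say that the plan's own figures show this handling deciding success. They do not. Full verification is assumed: section 8.2.1 reports 19% biopsied and roughly 15 to 20% with imaging follow-up. The 87% is also assumed to be a confirmed share. The 70% verdict changes only for a confirmed share between about 74% and 92%, given 24% PET-negative. The verified mix matters too. At 10% PET-negative and 87% confirmed, the figures are 0.783/0.883 = 88.7% and 78.3%, and both pass. If all 360 PET-negative men expected among 1,500 counted as misses beside the 285 verified positives, the figures would be 248/608 = 40.8% and 248/645 = 38.4%, and both fail. The illustration uses 375 because the success rule is limited to cases with follow-up or pathology.

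Nor would the formal hypothesis test change: the null of at most 50% is rejected at 66.1%. What is at risk is the 70% point-estimate rule. The mechanism does not carry over to the per-region analysis, which has no biochemical false-negative rule and leaves out PET-negative regions.

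**What to change.** In 8.3.2 d) i), write out the per-patient sensitivity formula. State that a false-positive patient with no true-positive lesion and with biochemical recurrence counts as not detected, and so is in the denominator, while remaining false positive for PPV. Apply the 70% rule to this version and report TP/(TP+FN) beside it for each reader.

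Add two sensitivity analyses:

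- One counts PET-positive men classed inevaluable as not detected, because they also leave the denominator.
- One leaves out men classed false positive only because PSA did not fall sufficiently after targeted treatment. In the illustration this analysis lies between 66.1% (none of the 37 so classed) and 73.4% (all of them).

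Men with an imaging-confirmed lesion and a pathology-refuted one are not covered by the new sentence, so the plan should say explicitly how they count.

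No new data are needed, and the change should be made before the central reads are analysed. The cost is a less favourable sensitivity, and some correctly located lesions labelled false positive through PSA non-response would count as misses in the main version.

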2.1 Primary

- Sensitivity on a per-patient and per-region-basis (Table 1) of ⁶⁸Ga-PSMA-11 PET for detection of tumor location confirmed by histopathology/biopsy, clinical and conventional imaging follow-up.

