8.2 Determination of Sample Size and Accrual Rate

8.2.1 Sample Size and Power Estimate

The primary endpoint is to evaluate the sensitivity on a (1) per-patient and (2) per-region-basis (prostate bed, pelvis, extrapelvic soft tissue, and bone metastases) of ^{68}Ga -PSMA-11 PET for detection of tumor location confirmed by histopathology/biopsy. Based on our first protocol in biochemical recurrent patients, we have updated the distribution of disease that we expect to find:

- a) Prostate bed: 15%
- b) Pelvis: 27%
- c) Extrapelvic soft tissue: 24%
- d) Bone metastases: 11%
- e) No evidence of disease on PSMA PET: 24%

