Of our first cohort of patients, 19% of patients underwent biopsy after a positive PSMA PET imaging. Based on biopsy results there was 100% sensitivity and 87% specificity. There were no True Negatives or False Negatives on biopsy. Imaging follow-up is not complete for our first study so we cannot estimate the percent of patients that will have imaging follow-up, but it appears that roughly 15 to 20% of patients will have imaging follow-up. Consistent with our second protocol, we anticipated that the sensitivity for the four regions and for all regions combined using conventional imaging ranges from 30-60%. An overall sensitivity for ^{68}Ga -PSMA-11 PET of at most 50% will be considered as unacceptably low. Hence, the null hypothesis that the sensitivity is at most 50% will be tested against the alternative hypothesis that the sensitivity is greater than 50%. It is hypothesized that ^{68}Ga -PSMA-11 PET imaging on the per-region and per-patient basis will substantially increase the sensitivity for the four regions to at least 70%. A sample size of 75 true positives is required for rejecting the null hypothesis that the sensitivity is at most 50% with 90% power at the one-sided 0.01 ($=0.05/5$ – a Bonferroni adjustment for evaluating the sensitivity for the four regions and for all regions combined) significance level, assuming an average regions specific prevalence of 20%. Although 19% of patients underwent biopsy and 15% of patients have imaging follow-up, we anticipate that the biopsy rate will fall in this study as referring clinicians become more comfortable with the imaging results. Therefore, we will combine imaging and biopsy follow-up in the primary aim, and will require 375 with both imaging and/or biopsy follow-up in order to power the analysis at a per region level. Assuming a prevalence rate of 20% for disease in each individual region, a total sample size of 1,500 patients is required. In summary, the proposed target accrual of 1,500 patients (375 with biopsies or imaging follow-up) will provide adequate power for detecting the anticipated improvement in the sensitivity for both the per-patient and per-region based ^{68}Ga -PSMA-11 PET imaging. However, a sample size of 107 patients with biopsies/follow-up in total is sufficient for detecting the anticipated improvement in sensitivity when evaluating per-patient based sensitivity.

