8.3 Analyses Plans

8.3.1 Analysis Population

Patients with histopathology correlates will be analyzed for the Primary Aim. All remaining patients will be analyzed for the secondary endpoints.

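### The primary per-patient sensitivity has no single denominator, and the false-negative rule, read literally, counts PET-negatives without follow-up while PET-positives must be verified

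*Combined protocol and SAP*

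**What the plan says.** Three descriptions of who counts in the primary per-patient sensitivity stand in the current text.

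- **Histopathology only.** Section 8.3.1: "Patients with histopathology correlates will be analyzed for the Primary Aim. All remaining patients will be analyzed for the secondary endpoints". The opening sentence of 8.2.1 stops at the same point, and the text then moves to expected disease distribution: "for detection of tumor location confirmed by histopathology/biopsy. Based on our first protocol in biochemical recurrent patients".
- **Composite.** Section 2.1, like the abstract and the first sentence of 8.3.2, defines sensitivity "for detection of tumor location confirmed by histopathology/biopsy, clinical and conventional imaging follow-up". Later in 8.2.1: "we will combine imaging and biopsy follow-up in the primary aim, and will require 375 with both imaging and/or biopsy follow-up". The success rule in 8.3.2 asks two of three readers to reach 70% per-patient sensitivity among cases with imaging follow-up, pathology or both.
- **PET-negatives with biochemical disease.** Section 8.3.2 d) i) (4) first requires positive pathology for a false negative, then adds that "patients without evidence of disease on PSMA PET but with biochemical evidence of disease will be considered a False Negative". It states no pathology or follow-up condition. The region-level rule has no such addition.

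Biochemical recurrence is an inclusion criterion (3.3.1) and is checked at screening (6.1.1.1). Under 8.3.2 b), a PET-positive finding is true positive, false positive or inevaluable, according to stated criteria.

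**The concern.** Under the literal false-negative rule the two arms of the sensitivity fraction are filled differently. A PET-negative patient enters the denominator because of the PSA that qualified him for the trial. A PET-positive patient enters only if pathology, imaging or clinical follow-up makes him a true positive; without such evidence he drops out. The estimate then measures the completeness of follow-up as well as the scan, and it falls as follow-up thins.

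There is also an overlap. A PET-negative patient with negative pathology and a raised PSA meets both the true-negative definition, d) i) (2), and the false-negative definition, d) i) (4).

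The 70% rule decides whether the primary endpoint is met, and section 1.1 intends the data for an NDA. A denominator that is still open when the central reads are analysed could be chosen with the result in view.

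**Working it through.** **The plan's own numbers.** With null 50%, alternative 70%, one-sided 0.01 and 90% power, the normal approximation gives n = [(2.326 x sqrt(0.25) + 1.282 x sqrt(0.21)) / 0.20]^2 = 76.6, close to the stated 75. Then 75/0.20 = 375, 75/0.70 = 107, and 375/1,500 = 25% followed (implied, not stated). The sample size is not disputed here.

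**Inputs from 8.2.1.** 1,500 patients; 375 with biopsy and/or imaging follow-up; 24% PET-negative. So PET-negative = 0.24 x 1,500 = 360 and PET-positive = 1,140.

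**Assumption.** 87-100% of evaluable PET-positives are true positive (TP), and all followed PET-positives are evaluable unless stated. The first cohort's 87% is labelled specificity, but "There were no True Negatives or False Negatives on biopsy", so it is read here as a confirmation rate. Paired results below are for 87% and 100%. Sensitivity = TP/(TP+FN), where FN is false negatives.

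**A. Literal rule, FN = 360**
- Followed patients PET-negative in proportion (285 PET-positive): 248/608 = 41%; 285/645 = 44%.
- All 375 followed are PET-positive: 326/686 = 47.5%; 375/735 = 51%.
- Some PET-positives can qualify without follow-up imaging: bone by a baseline correlate, bone and prostate bed by a PSA fall after targeted treatment. From the 8.2.1 distribution these are (11+15)/77 of PET-positives. If every unfollowed one qualified, at 100% confirmation: 26/77 x (1,140-285) = 289, giving 574/934 = 61%; or 26/77 x (1,140-375) = 258, giving 633/993 = 64%.
- That is not a strict ceiling. Visceral lesions share the PSA-fall route, but 8.2.1 does not separate them from extrapelvic nodes. If every unfollowed extrapelvic patient qualified too (50/77), the result would be 840/1,200 = 70% or 872/1,232 = 71%.
- In general, 70% needs 360 x 0.7/0.3 = 840 TP. That is 840/1,140 = 74% of PET-positives verified at 100% confirmation, or (840/0.87)/1,140 = 85% at 87%.

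**B. Followed cases only**
- 24% of the 375 PET-negative (FN = 90): 248/338 = 73%; 285/375 = 76%.
- Half of the 375 biopsied and all PET-positive, half imaged with 24% PET-negative (FN = 45): 287/332 = 86%; 330/375 = 88%.
- 10% PET-negative (FN = 37.5): 294/331 = 89%; 337.5/375 = 90%.
- In the other direction, 35% PET-negative gives 62-65%; with 24% PET-negative and only 75% of followed PET-positives evaluable, 67-70%.

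**C. Histopathology only.** About 100% if biopsy again yields no false negatives.

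**Everyone followed.** A and B coincide: 992/1,352 = 73%; 1,140/1,500 = 76%.

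**The case against.** The strongest reply is that the text can be read coherently. Section 8.2.1 says outright that biopsy and imaging will be combined, and histopathology-only sensitivity is a separate secondary objective (2.2; 8.3.3 item 2), so it cannot sensibly also be the primary. The success rule in 8.3.2 can be taken to select patients, with d) i) (4) only labelling those selected. The introduction to 8.3.2 d) ranks pathology above imaging and clinical follow-up, which would settle the true-negative overlap. And 8.3.2 b) says all patients will have follow-up imaging, in which case rules A and B agree.

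Much of this stands. A reader might infer that histopathology-only is an equally live primary analysis; the documents do not support that, and 8.3.1 and the opening of 8.2.1 look like carry-over. A reader might also infer that nothing ranks pathology against the biochemical rule; that is too strong, although the ranking does not clearly reach a PSA recorded at entry.

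What does not stand is the claim that the restriction is already written. No section says that the success rule limits d) i) (4). Nor does the sample-size section plan for full follow-up: it expects that "roughly 15 to 20% of patients will have imaging follow-up" and sizes the trial on 375 followed patients in 1,500.

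**Conclusion.** The inconsistency is real and should be corrected before the central reads are analysed. The histopathology-only wording is a drafting conflict with a clear intended answer. The unrestricted false-negative rule is the consequential part: on the same scans it can put the result at about 41-51% (61-64% with the bone and prostate-bed allowance), against 73-76% for followed cases, or 86-90% if fewer of those are PET-negative. The mark is 70%.

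These sizes are illustrations. They rest on 375 of 1,500 followed, the earlier protocol's 24% PET-negative share, and an assumed 87-100% confirmation rate.

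Two stronger conclusions are tempting. One is that the trial will fail its endpoint; that needs the literal reading together with sparse follow-up. The other is that followed cases clear 70% only narrowly. That depends on 24% of *followed* patients being PET-negative, a share the plan never states. Biopsies in the first cohort followed a positive PET, so the share is likely to be lower, although "we anticipate that the biopsy rate will fall in this study" moves it back up.

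**What to change.** 1. Rewrite 8.3.1 and the first sentence of 8.2.1 so that the primary set is the composite set of the 8.3.2 success rule. Reserve the histopathology subset for the secondary endpoint.
2. In 8.3.2 d) i) (4), state that in the primary analysis the biochemical rule applies only to PET-negative patients within that set. State its order relative to the negative-pathology true-negative rule, consistently with the pathology ranking in 8.3.2 d). Do not delete the rule: 8.3.2 b) gives no imaging-based false-negative criterion, so sensitivity would drift towards 100%.
3. Keep true positives established by clinical follow-up or a baseline bone correlate in the primary analysis, as the abstract, 2.1 and 8.3.2 provide, and say so in the definition of the set. Use the follow-up windows already given for each lesion type. Because this route is open only to PET-positives, add a sensitivity analysis without them. In case B with 24% PET-negative, admitting all 11/77 x 855 = 122 unfollowed bone patients would raise 73-76% to 80-82% (370/460; 407/497).
4. Add two further sensitivity analyses: all PET-negatives as false negatives; and weighting by the inverse of the verified fraction within PET result, stating the untestable assumption that verification is unrelated to disease status given PET result. Report followed, unfollowed and inevaluable numbers by PET result.

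**Cost.** Wording in three places and analyses on data already planned. In the illustration at 87%, the Wilson 95% interval widens from about +/-3.9 points (n = 608) to about +/-4.7 (n = 338). Giving negative pathology precedence removes some false negatives, which favours the agent. The result will still depend on who is followed and who is evaluable; the change makes that visible but does not remove it.
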